2.3.2 KNOWN POTENTIAL BENEFITS

Direct benefits:

Participants may benefit from enhanced HIV treatment services tailored to adolescents. This could result in better retention, adherence, and viral suppression. Clinics and HCWs may benefit from increased time and resources efficiencies from the stepped care approach.

Indirect benefits:

The study may produce data that will lead to improved interventions for treatment and care of adolescents with HIV, thus a benefit to society.

2.3.3 ASSESSMENT OF POTENTIAL RISKS AND BENEFITS

All adult study participants will have the study and relevant study procedures explained to them, their questions answered, and provide written consent for their enrollment.

Together, the UW, Nairobi, and Kisumu Study Team has more than 10 years' experience managing HIV-infected children and adolescents and in clinical trials and observational research and will take every precaution to protect participants' and their caregivers' confidentiality. All study staff will have been trained in the Protection of Human Subjects and new staff will receive similar training.

Procedures to minimize physical risks: There are no medical interventions associated with the study, therefore we anticipate no risk of serious harm to study participants.

Procedures to minimize confidentiality risks: All key personnel will be trained in the Protection of Human Subjects. The field team will take every precaution to protect participants' confidentiality. We will only collect personal identifiers for the purposes of identifying and contacting participants about the study. This information will include the names, telephone numbers and emails for those identified as interested in participating in the study. Personal identifiers will be used to contact stakeholders in aim 1 and HCWs to remind them of their scheduled study activities. This information will also be used to contact them again to verify the accuracy of the information

Adapted from NIH Behavioral and Social Intervention Clinical Trial Protocol Template v3.0 - 20180827

collected or to elaborate or clarify certain information provided during study procedures if they select the option to be re-contacted on the consent form.

All participants will be assigned a study identification number (ID). Participant identifiers will be linked to their study ID in a link-log document that will be stored separately from all other study data. Only necessary study staff will have access to this document and will not share this information with other study staff or with others outside of this study.

Procedures to minimize psychological risks: All participants will be assured that their participation is voluntary and that they may withdraw from the study at any time. Kenyan study personnel experienced in research with adolescents will be available for questions when participants take the surveys. While there is a risk of discomfort related to answering sensitive questions about sexual behavior, mental health, and stigma on the surveys, these questions are similar to what would be asked as part of routine HIV care for adolescents. Survey participants will be informed that they can skip any question or stop the interview at any time. Any participant who reports emotional distress, exposure to violence, or other threat will be offered support or referral to additional services, as appropriate, according to standard operating procedures. Some younger adolescents receiving HIV care and taking ART (which may be called 'medicine' and not HIV medicine) may not yet know their HIV status, because the caregiver is not ready for the child to learn this information. The ALHIV surveys will not include specific mention of HIV or ART unless a participant reports knowledge of their own HIV status on a screening question. This approach will minimize the possibility of involuntary disclosure to an ALHIV and maximize representative enrollment.

Procedures to minimize other risks: Study staff will be trained to take all precautions to ensure confidentiality of participation and data collected and will have standardized operating procedures (SOPs) to follow to minimize the risks of a participant's loss of confidentiality. Risk of breach of confidentiality of study data is low, as all patient data collected will not include names and will be located on a password protected secure study server. ALHIV participants will be assured that their sensitive information will not be shared with anyone outside the study team, including a parent, caregiver, or partner who may be present. Study staff will be trained in the importance of confidentiality during training prior to study implementation. The community-driven process of adaptation and optimization of the intervention to local context will ensure that the intervention is culturally sensitive before implementation in the pilot and RCT. All HCW participants will be assured that their participation will not affect their employment status.

Procedures to minimize unexpected events, including social harms, including violence: We will minimize social harms by training study staff on how to counsel participants on ways to avoid harm as per national guidelines, including not disclosing their HIV status to anyone who may harm them. We will also inform participants that they can contact study staff using the number provided on the consent form if they experience social harms. We will refer participants to the appropriate clinic staff, as needed.

There are no mandatory reporting requirements in Kenya for studies that ask about gender-based violence. If a participant reports directly to a study staff that they are experiencing violence or other threat, we will follow study SOPs to refer that person to a clinic staff person for appropriate follow-up services. If they report violence or other threat on the self-administered survey, a

Adapted from NIH Behavioral and Social Intervention Clinical Trial Protocol Template v3.0 - 20180827

message will appear that recommends a referral and that our study staff could help with that referral if they choose. As part of routine practice, HIV care clinicians are expected to ask adolescent clients about exposure to violence and are mandated to perform the relevant tests and offer care and referrals to legal and medical resources. There will be no mention of HIV on adolescent recruitment talking points or consent and assent forms for surveys. Adolescent surveys will not include specific mention of HIV or ART unless a participant reports knowledge of their own HIV status on a standardized set of screening questions. If we learn of social harms related to routine HIV care (and not this study), we will follow our standard operating procedures and clinic guidelines to offer referrals to the appropriate counseling or services.

Study justification

UNAIDS ‘95-95-95’ targets cannot be achieved without additional support for ALHIV to increase retention in care and to support viral suppression. Risk prediction tools as well as a stepped care approach to care can support differentiation of ALHIV to different risk groups, and tailor care based on risk.

Our team has conducted formative work with ALHIV, caregivers, HCW and policy makers and has developed and validated a clinical prediction tool to identify ALHIV at highest risk of not being retained in care and poor viral suppression that could be adapted to identify adolescents who may need more support in their care. Understanding how best to use the risk prediction tool as well as how to tailor services based on risk may ultimately result in more efficient HIV care services, as well as adequate support for ALHIV at highest risk of poor outcomes.

A data-driven, provider-led, health systems intervention can identify adolescents most at risk for loss to care, sub-optimal adherence, and viral failure. Our stepped care approach, combined with a clinical prediction tool, is a timely and flexible intervention in the context of differentiated care and numerous ongoing care initiatives. By improving adolescent engagement in care and optimizing provision of limited resources, this intervention can ultimately improve health and decrease HIV transmission risk among adolescents in Kenya. Improved models of data-informed, client-centered care are urgently needed for this population and may translate to other programs in Kenya, and more generally in sub-Saharan Africa.

3 OBJECTIVES AND ENDPOINTS

OBJECTIVES	ENDPOINTS	JUSTIFICATION FOR ENDPOINTS

Primary
 
Aim 1: To develop, adapt, pilot, and optimize implementation of a data-informed stepped care (DiSC) intervention for ALHIV treatment management.
	
DiSC intervention
	
To provide intervention for the trial

OBJECTIVES	ENDPOINTS	JUSTIFICATION FOR ENDPOINTS
Aim 2: To evaluate effectiveness of the DiSC intervention on ALHIV retention in care in up to 24 high-volume HIV clinics in Kenya.	Retention in care	Marker of successful HIV care
Secondary		
Aim 1: To determine acceptability, feasibility, adaptability and fidelity of the DiSC intervention	Pilot acceptability, feasibility, adaptability and fidelity	Pilot data to inform intervention adaptations
Aim 2: To evaluate effectiveness of the DiSC intervention on ALHIV cascade outcomes (adherence and viral suppression) and adolescent self-efficacy and correlates of outcomes in up to 24 high-volume HIV clinics in Kenya	ART adherence Viral suppression ALHIV self-efficacy	Markers of successful HIV care Covariate, mediator data
Aim 2: To evaluate effectiveness of the DiSC intervention on health service outcomes in care in up to 24 high-volume HIV clinics in Kenya	Client wait time Costs	Impact of intervention on service delivery
Aim 2: To evaluate effectiveness of the DiSC intervention on implementation outcomes in care in up to 24 high-volume HIV clinics in Kenya	Feasibility, acceptability, adaptation, fidelity, adoption, reach, maintenance	Intervention delivery data to support effectiveness data Mediator data

4 STUDY DESIGN

[figure not shown]
4.1 OVERALL DESIGN

In aim 1, with relevant stakeholders in adolescent HIV, we will collaboratively develop the DiSC intervention, then adapt and pilot test the intervention.

In aim 2, we will conduct a cluster randomized trial (cRCT) in up to 24 sites in western Kenya (12 randomized to intervention and 12 to control) (Figure 1).

Figure 1: Study design, main activities, and outcomes

Adapted from NIH Behavioral and Social Intervention Clinical Trial Protocol Template v3.0 - 20180827

Study hypothesis

- Primary and secondary outcomes: We hypothesize that the DiSC intervention will result in better retention, adherence and viral suppression among adolescents in the intervention sites compare to those in control sites. Hypothesized psychosocial outcomes will include better psychosocial and family support, mental health, family support and adolescent self-efficacy.
- We hypothesize the DiSC intervention will be associated with improved clinic efficiency (client wait time), and will be cost effective.
- The DiSC Intervention will be feasible, acceptable to HCW and adolescents but will require clinic specific intervention adaptations.

Randomization

Up to 24 clinics will be randomized in a 1:1 ratio using computer generated random numbers to either intervention or control, using restricted randomization to balance by county, aiming to balance the numbers of clinics from each county between arms. Timing of randomization will be prior to study start. Randomization will be done at the University of Washington by a biostatistician not involved in study procedures. A list of clinics with their allocation arms will be sent to the study team. We will perform individual substitutions of sites on a case by case basis, as needed (e.g. if the site no longer meets an eligibility criterion). The intervention is administered at the clinic-level; it is not possible to blind participating clinics or study team members.

Study intervention

The DiSC intervention is comprised of a system to assign adolescents to care based on their health needs and the different levels of care for each assignment group. Control sites will continue with standard of care approaches for adolescent clinic visits (usually 1-3 monthly visits) regardless of health care needs and additional support as needed.

Analysis

Adapted from NIH Behavioral and Social Intervention Clinical Trial Protocol Template v3.0 - 20180827

We do not plan for interim analysis. Subgroup analysis (age and gender) are planned as described in the statistical analysis section.

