5.4 SCREEN FAILURES

Screen failures are defined as clinics that are not included in the final list of clinics for randomization. After randomization, we do not anticipate to re-screen or include additional facilities.

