7.1 DISCONTINUATION OF STUDY INTERVENTION/EXPERIMENTAL MANIPULATION

We do not anticipate that clinics will discontinue participation or withdraw from the study after randomization. However, if this occurs, the study team will get permission from the clinic to use study data up until the time of discontinuation.

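### Protocol 4.1 allows discretionary clinic substitution with no stated limit to the period before allocation is released and no safeguard against arm-dependent replacement

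*Protocol*

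**What the plan says.** The Randomization paragraph of Protocol 4.1 sets out the sequence. Up to 24 clinics are allocated 1:1 by a biostatistician who has no part in study procedures, "using restricted randomization to balance by county, aiming to balance the numbers of clinics from each county between arms". On timing it says only: "Timing of randomization will be prior to study start". It continues: "A list of clinics with their allocation arms will be sent to the study team". The next sentence is the substitution rule: "We will perform individual substitutions of sites on a case by case basis, as needed". A parenthesis then offers one example, a site that has ceased to satisfy an eligibility criterion. The paragraph closes by saying that "it is not possible to blind participating clinics or study team members".

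Three other protocol sections bear on the same event:

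- Section 5.4: "After randomization, we do not anticipate to re-screen or include additional facilities".
- Section 7.1: "We do not anticipate that clinics will discontinue participation or withdraw from the study after randomization". If one does, its data up to that date are used with the clinic's permission. Replacement is not mentioned.
- Section 9.3 specifies intent-to-treat and says nothing about replaced or replacement clinics.

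The SAP does not mention substitution. Its accrual list (3.1) and trial profile (3.2) have no line for a replaced clinic.

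**The concern.** A clinic that enters because someone chose it, knowing which arm has the vacancy, is not placed by the random process that justifies the comparison. The same holds for a clinic removed with its arm known. The text order puts the substitution rule after release of the list, to a team that cannot be blinded, and nothing limits it to an earlier time.

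The eligibility example does not close the gap. It is only an example, and the clinic criteria in Protocol 5.1 include being willing to participate. A clinic that learns its arm and then declines has stopped meeting a criterion. Intervention clinics take on stepped-care delivery and twice-monthly meetings (Protocol 6.2.1), so loss of willingness could well differ by arm.

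Substitutes might also differ from the clinics they replace. Protocol 5.5 draws the 24 from a frame of 55 as the eligible, willing clinics with the highest enrolment. If replacements came from the other 55 − 24 = 31, they would be clinics passed over for lower enrolment, ineligibility or unwillingness. Some of the 55 took part in the earlier phase, so the team may know how some of them perform. With 12 clinics per arm, each carries one twelfth of its arm's mean in a clinic-level comparison.

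**Working it through.** **What is specified.** Read together, Protocol 4.1, 5.4, 7.1 and 9.3 and SAP 3.1 and 3.2 leave these items without an answer: who approves a substitution, by when, from which list and in what order, how the substitute receives its arm, whether county balance is kept, and whether the replaced clinic, the substitute or both are analysed.

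**Which between-clinic variation to use.** The documents use two measures, so I checked which one each table follows.

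- Protocol Table 3a (75% against 93%, 100 per clinic, coefficient of variation k = 0.15) states 10 facilities per arm. The Hayes–Bennett formula is c = 1 + (1.96 + 0.84)² × [p₁q₁/m + p₂q₂/m + k²(p₁² + p₂²)]/(p₁ − p₂)². It gives 9.39, which rounds up to 10 and matches.
- The facilities-per-arm table in SAP 2.2.2 (75% against 90%, 150 per clinic, 0.10) states 11. Reading 0.10 as an intraclass correlation (ICC): 7.85 × (0.1875 + 0.09)/0.15² × (1 + 149 × 0.10)/150 = 10.3, which rounds up to 11 and matches. Reading it as a coefficient of variation (CV) gives 7.

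The SAP table therefore behaves as an ICC table, although the SAP text and the table's footnote call 0.10 a coefficient of variation. Both readings are carried below.

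**Worst-case illustration.** Inputs from the documents are 75% retention, 12 clinics per arm and 150 per clinic. The assumptions, which are not in the documents, are: no true effect; normally distributed clinic means; in one arm only, the clinics with the lowest true retention are replaced by average ones; the standard error stays at its unselected value.

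- Between-clinic SD: √(ICC × 0.75 × 0.25) or CV × 0.75.
- SE of the arm difference: √[2 × 0.1875 × (1 + 149 × ICC)/(150 × 12)] or √[2 × (SD² + 0.1875/150)/12].
- The lowest of 12 standard normal values is on average 1.63 below the mean, and the lowest two together 2.74 below. The shift b is therefore 1.63 × SD/12 or 2.74 × SD/12.
- Two-sided type I error: Φ(−1.96 + b/SE) + Φ(−1.96 − b/SE).

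| Reading | SD (points) | SE (points) | Lowest one replaced | Lowest two replaced |
|---|---|---|---|---|
| CV 0.10 | 7.5 | 3.39 | 1.0 points, 6.0% | 1.7 points, 8.0% |
| CV 0.15 | 11.25 | 4.81 | 1.5 points, 6.2% | 2.6 points, 8.3% |
| ICC 0.10 | 13.7 | 5.76 | 1.9 points, 6.2% | 3.1 points, 8.4% |

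Example at ICC 0.10: SD = √0.01875 = 0.137; SE = √(2 × 0.1875 × 15.9/1800) = 0.0576; b = 1.63 × 13.7/12 = 1.86 points, or 0.32 SE. At the SAP's other value, ICC 0.15, the SD is √(0.15 × 0.1875) = 16.8 points. The shifts become 2.3 and 3.8 points, with type I error 6.2% and 8.5%. The points move with the reading; the error rates hardly do.

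**Milder case.** At CV 0.15, one clinic replaced by one that is one between-clinic SD better gives a shift of 11.25/12 = 0.9 points and a type I error of 5.4%. A swap unrelated to retention has an expected shift of zero.

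**The case against.** The best defence is that this is a sensible contingency rule for a pragmatic trial. The one reason it names is eligibility, and several clinic criteria are objective: an active EMR system, roughly 150 adolescents in care, no overlapping study. Randomisation precedes study start, so a swap could happen before any trial outcome exists. The 55-clinic frame and the highest-enrolment rule in 5.5 suggest where a replacement would come from and in what order. A neutral swap on those grounds does little harm.

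Much of this stands, and it rules out several stronger readings that a reader might infer:

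- **That the rule breaks the randomisation.** Its timing after release is inferred from sentence order and from the wording of the example; it is not stated. The documents support only that the rule can undermine the randomisation, because nothing prevents it.
- **That 4.1 contradicts 5.4.** Section 5.4 expresses an expectation and does not forbid additions. Section 7.1 uses the same form and then provides for the unexpected case. The sections need reconciling.
- **That intent-to-treat is abandoned.** No section says the replaced clinic leaves the analysis, or that its substitute is placed without randomisation. Both points are simply unspecified.

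The defence does not answer three things. The example leaves the list of reasons open, willingness is one of the criteria, and neither document ties a replacement to the enrolment ranking or to a decision made blind to arm.

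**Conclusion.** The point holds as a gap in safeguards. An unblinded team has open discretion to substitute clinics, no limit to the period before release is stated, and even the eligibility ground admits reasons that depend on the arm. This should be corrected.

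The size depends on how selective any substitution is, which the documents cannot tell us. It ranges from no expected bias for a neutral swap to the worst case of about 1.0 to 1.9 points (one clinic) or 1.7 to 3.1 points (two clinics), from CV 0.10 to ICC 0.10, with type I error of about 6% or 8%. That worst case assumes that the truly lowest clinics in one arm are identified and removed. It illustrates the exposure and does not predict what the team would do.

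**What to change.** Replace the discretionary rule in Protocol 4.1 with the following, and align 5.4, 7.1, 9.3 and the SAP with it:

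1. **Before allocation is released:** a clinic found ineligible or unwilling may be replaced. The independent biostatistician takes the next clinic from a pre-ranked reserve list for the same county, for example the 55-clinic frame ordered by adolescent and young adult enrolment. The decision to replace is made blind to arm, and list position alone determines the substitute.
2. **After release:** no replacements. Every randomised clinic stays in the intent-to-treat analysis in its allocated arm, with all EMR data that can be obtained, subject to the clinic's permission under 7.1. This is feasible because the primary outcome comes from routine EMR data (SAP 2.1).
3. **If a substitution has already occurred:** report its date, reason and arm in the CONSORT diagram, and add a sensitivity analysis restricted to the originally randomised clinics.

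A pre-ordered reserve list with a blinded decision after release would also give much of the protection, but a ban is simpler to verify. The cost is protocol and SAP wording, the effort to secure permission from a departing clinic, and a small loss of power because a clinic that leaves is not replaced. If one clinic's data were lost entirely, the SE would rise by the factor √[(1/11 + 1/12)/(2/12)] = 1.022, about 2%.

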4.2 SCIENTIFIC RATIONALE FOR STUDY DESIGN

A cRCT design is appropriate because the intervention will be administered at the clinic level.

4.3 JUSTIFICATION FOR INTERVENTION

The intervention will be delivered by HCW during routine clinical visits; and works at improving clinic level effectiveness in care management. We anticipate at least 50 adolescents per site will be exposed to the intervention during the course of the study period. The intervention will be offered during regular clinic visits that are typically scheduled 1-6 monthly.

4.4 END-OF-STUDY DEFINITION

The definition of the end of the study is: completion of the 12-month follow-up assessment shown in the Schedule of Activities (SoA), Section 1.3.

5 STUDY POPULATION

Aim 1

Intervention development: Policy makers at national, county and care partner levels, HCW, ALHIV and caregivers as well as other stakeholders in HIV care will be invited to participate in an intervention development workshop.

HCWs in 2 facilities participating in the completed formative phase of the study will pilot the intervention in their clinics.

Aim 2

Cluster RCT: We will conduct this study at up to 24 HIV care and treatment facilities located in Kisumu, Homa-Bay, Migori County.

The population of interest is ALHIV age 10-24 enrolled in participating clinics, caregivers of adolescents and young adults and HCW offering services. The intervention will be administered by existing HCW, who will also participate in implementation surveys, interviews, and focus groups to assess health service and implementation outcomes. A cohort of ALHIV ages 10-24 years will also be enrolled to participate in longitudinal surveys. A subset of ALHIV and caregivers of ALHIV will also complete satisfaction surveys at the end of the trial.

